If a patient experiences DLT (for definition refer to [Table 4.1.4.1:2](#)), therapy may be continued at a reduced dose (for dose reduction, refer to [Table 4.1.4.3:1](#)) after recovery of the respective adverse event(s) to pre-dose CTCAE grade(s). The investigator shall liaise with BI and ask for confirmation of the dose of the trial drug before a new treatment course is started for any patient. In questionable cases, the DMC might be involved in decision making. If a patient is not eligible for further therapy, the patient has to discontinue further treatment with the trial drug.

Proprietary confidential information.

© 2017 Boehringer Ingelheim International GmbH or one or more of its affiliated companies. All rights reserved.

This document may not - in full or in part - be passed on, reproduced, published or otherwise used without prior written permission.

Table 4.1.4.1:2 Dose limiting toxicities

Dose limiting toxicity (DLT)

DLTs are defined as any of the following events that are considered related to afatinib:

1. CTCAE grade 4 hematologic toxicity lasting for 7 days
 2. CTCAE Grade 3 or 4 non-hematologic toxicity (except fever grade 3).
 3. CTCAE Grade 2 or higher decrease in cardiac left ventricular function
 4. CTCAE Grade 2 or higher worsening of renal function as measured by serum creatinine, newly developed proteinuria, or newly developed decrease in glomerular filtration rate
 5. CTCAE Grade 2 diarrhoea persisting for 7 or more days, despite supportive treatment (loperamide treatment or other effective anti-diarrhoeal medication)
 6. CTCAE Grade 2 nausea and/or vomiting persisting for 7 or more days despite antiemetic treatment
 7. CTCAE grade 5 events
-

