4.1.4.3 Dose reduction of afatinib

Treatment related toxicities will be managed by treatment interruptions and subsequent dose reductions of afatinib according to the schedule described in [Table 4.1.4.3: 1](#). Dose reductions will apply to individual patients only. Once the treatment dose has been reduced, it cannot be increased later.

To prevent the development of more severe adverse events, treatment related diarrhoea, nausea and vomiting or rash should be managed early and proactively as described in [Section 4.2](#).

Proprietary confidential information.

© 2017 Boehringer Ingelheim International GmbH or one or more of its affiliated companies. All rights reserved.

This document may not - in full or in part - be passed on, reproduced, published or otherwise used without prior written permission.

Table 4.1.4.3:1 Dose reduction scheme for afatinib

AE type and CTCAE Grade	Action	Dose reduction scheme

Events related to study drug:
 
 • Diarrhoea Grade 2 persisting for 7 or more consecutive days despite adequate anti-diarrhoeal medication/hydration • Reduced renal function to \geq Grade 2 as measured by serum creatinine, proteinuria or decrease in glomerular filtration rate of more than 50% from baseline • Any drug related AE Grade \geq3 	
Pause treatment until patient has recovered to Grade \leq1 or baseline¹.
 
Resume treatment at reduced dose according to schedule opposite.
 
If patient has not recovered to Grade \leq1 or baseline¹ within 14 days, study treatment must be permanently discontinued².
	
If patient was treated at dose level 3, resume treatment at dose level 2
 
If patient was treated at dose level 2, resume treatment at dose level 1
 
If patient was treated at dose level 1, resume treatment at dose level 0
 
If patient was treated at dose level 0, resume treatment at dose level -1
 
If patient was treated at dose level -1, discontinue afatinib.

Acute onset and/or unexplained worsening of pulmonary symptoms (dyspnoea requiring supplementation of oxygen with cough and/or fever)
	
Pause afatinib while clinical assessment to exclude ILD is completed.
	
If ILD is ruled out as a cause of symptoms, grade symptoms and relatedness and report as AEs. If AEs are not related, resume afatinib at current dose.
 
If ILD is confirmed, discontinue afatinib.

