
Acute onset of symptoms indicative of keratitis
	
Pause afatinib while clinical assessment of keratitis is ongoing.
	
If a diagnosis of ulcerative keratitis is confirmed, treatment with afatinib should be discontinued. Unless the treatment benefit for the patient outweighs the risks of worsening keratitis (blindness) in the opinion of the investigator.

Acute onset of symptoms indicative of cardiac failure and/or CTCAE Grade \geq 2 LVEF decrease and/or \geq20% decrease of LVEF from baseline
	
Pause afatinib while clinical assessment is ongoing and until patient recovers to Grade \leq1 or baseline¹
	
If patient has not recovered despite appropriate treatment to Grade \leq1 or baseline¹ within 14 days, study treatment must be permanently discontinued²

1 Baseline is defined as the CTCAE Grade at the start of treatment

2 In the event that the patient is deriving obvious clinical benefit according to the investigator's judgement, further treatment with afatinib will be decided in agreement between the sponsor and the investigator.

In the event of any unrelated adverse events, the investigator may choose to interrupt the medication for up to 14 days, but no dose reduction should occur once treatment is resumed.

Proprietary confidential information.

© 2017 Boehringer Ingelheim International GmbH or one or more of its affiliated companies. All rights reserved.

This document may not - in full or in part - be passed on, reproduced, published or otherwise used without prior written permission.

If the medication is interrupted for more than 14 days, the decision to continue with afatinib will be made by the BI clinical monitor in agreement with the investigator.

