© 2017 Boehringer Ingelheim International GmbH or one or more of its affiliated companies. All rights reserved.

This document may not - in full or in part - be passed on, reproduced, published or otherwise used without prior written permission.

wound healing. If afatinib is interrupted for more than 14 days, the decision to continue will be made by the BI Clinical Monitor in agreement with the investigator.

Emergency procedures

Careful assessment of all patients with an acute onset and/or unexplained worsening of pulmonary symptoms (dyspnoea, cough, fever and demand for oxygen supplementation) should be performed to exclude interstitial lung disease (ILD). Study drug should be interrupted pending investigation of these symptoms. If interstitial lung disease is diagnosed, study drug must be permanently discontinued and appropriate treatment instituted as necessary.

Patients who present with symptoms of keratitis, such as acute or worsening eye inflammation, lacrimation, light sensitivity, blurred vision, eye pain and/or red eye should be referred promptly to an ophthalmic specialist. If a diagnosis of ulcerative keratitis is confirmed, treatment with afatinib should be interrupted or discontinued. If keratitis is diagnosed, the benefits and risks of continuing treatment with afatinib should be carefully considered. Afatinib should be used with caution in patients with a history of keratitis, ulcerative keratitis or severe dry eye. Contact lens use is a risk factor for keratitis and ulceration.

In case the patient develops acute onset of symptoms indicative of cardiac failure and/or CTCAE Grade ≥ 2 LVEF decrease and/or $\geq 20\%$ decrease of LVEF from baseline, study drug should be interrupted pending investigation of symptoms. The patient should be monitored closely for recovery. If patient has not recovered despite appropriate treatment to Grade ≤ 1 or baseline within 14 days study treatment must be permanently discontinued.

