4.2.2 Management of expected adverse events

At occurrence of a drug related AE:

- Pause the drug if applicable, refer to [Table 4.1.4.3:1](#)
- Treat the side effect
- Dose reduce at reintroduction if applicable

Dermatologic adverse events and diarrhoea are the most common side-effects associated with treatment with afatinib in the adult population. Treatment of these side-effects should be proactive and should be started as early as possible after onset of symptoms.

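### Protocol Section 4.2.1 orders a permanent stop for a cardiac or LVEF event unrecovered at 14 days; footnote 2 of Table 4.1.4.3:1 lets the same child continue

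*Protocol*

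**What the plan says.** Four places in the protocol bear on a child whose cardiac or LVEF event has not resolved.

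- **Section 4.2.1, emergency procedures.** The drug is interrupted during investigation. If the child has not recovered to Grade ≤1 "or baseline within 14 days study treatment must be permanently discontinued". There is no exception and no pointer to the dose-reduction table.
- **Section 3.3.4.1, item 6.** Study medication is to be discontinued on a diagnosis of heart failure, including a clinically relevant LVEF reduction. The item cites Section 4.2.1 and has no 14-day window.
- **Table 4.1.4.3:1, LVEF row.** Afatinib is paused. If the child has not recovered "within 14 days, study treatment must be permanently discontinued". Here the stop carries the marker for footnote 2. Under that footnote, if the investigator judges that the patient has obvious clinical benefit, "further treatment with afatinib will be decided in agreement between the sponsor and the investigator".
- **Section 4.1.4.3, text after the table.** This follows the sentence on unrelated adverse events. For an interruption of more than 14 days, "the decision to continue with afatinib will be made by the BI clinical monitor in agreement with the investigator". No benefit condition is stated.

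**The concern.** Section 4.2.1 and the LVEF row describe the same event and differ only at the point of decision. One makes the stop absolute; the other makes it conditional. An investigator who reads 4.2.1 would stop. An investigator who reads the table could ask the sponsor to agree to continue. Each could cite the protocol.

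This is a safety stopping rule in a trial that Section 2.3 calls first in child. The same section lists left ventricular dysfunction among the toxicities to be detected early. What is at stake is consistent handling of such a child, and whether a decision to continue counts as following the protocol.

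**Working it through.** No arithmetic applies: the documents give no rate for this event and the point rests on no sample size or error rate. The check is a comparison of texts.

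**Step 1. The two rules side by side.**

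| Element | Section 4.2.1 | LVEF row, Table 4.1.4.3:1 |
|---|---|---|
| Trigger | Cardiac-failure symptoms, Grade ≥2 LVEF decrease, or ≥20% fall from baseline | Same three |
| First action | Interrupt while investigating | Pause while assessing |
| Recovery target | Grade ≤1 or baseline | Same |
| Limit | 14 days | 14 days |
| Not recovered | Permanent stop, no exception | Permanent stop, subject to footnote 2 |

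Only the last line differs. Neither rule is limited to drug-related events, so neither is the more specific.

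**Step 2. What each course of action satisfies at day 14.**

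- No obvious benefit: both texts require a stop, so there is no conflict.
- Obvious benefit, decision to stop: 4.2.1, item 6 and the table are all satisfied. Footnote 2 permits continuation and does not require it.
- Obvious benefit, agreement to continue: footnote 2 is satisfied and 4.2.1 is breached. Item 6 is breached as well if heart failure is diagnosed or the reduction is clinically relevant.

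The conflict lies wholly in the third case.

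**Step 3. Does another text settle it?** Item 6 cites 4.2.1. In the other direction, Section 5.2.2.1 sends drug-related adverse events of special interest to Section 4.1.4.3. These include dose-limiting toxicities, and a related Grade ≥2 fall in left ventricular function is one (Table 4.1.4.1:2, criterion 3). A related Grade ≥2 event can therefore reach either rule. No text states precedence.

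**Step 4. Other routes to continuation.** Row 1 of the table covers "Any drug related AE Grade" 3 or above, and its 14-day stop also carries footnote 2. Removing the marker from the LVEF row alone would leave the exception open for a related Grade ≥3 cardiac event. For an unrelated event, the sentence after the table gives a further route by agreement with the sponsor's clinical monitor.

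**Step 5. Effect on the analysis.** SAP Section 7.4.2 computes the response rate on all treated patients. In SAP Table 6.2:1, deviation C3 (dose handling after an adverse event) excludes nobody. The response rate, analysis sets and sample size do not depend on which rule is followed.

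**The case against.** The best defence is that Section 4.2.1 is a condensed copy of the table row that lost its footnote markers. The wording is close. Elsewhere the protocol often leaves interruptions beyond 14 days to agreement: unrelated events, palliative radiotherapy, surgery, and diarrhoea with clinical benefit. This reading is possible, and the documents do not rule it out. Two things weaken it. Section 4.2.1 writes out flexibility for radiotherapy, surgery and keratitis but not for LVEF. The diarrhoea table repeats the clinical-benefit exception in full where it is meant to apply. Item 6 also points towards stopping.

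It is also fair to say that no site can continue alone, because footnote 2 needs the sponsor's agreement, and that the event is probably rare. Both points stand. They limit the size of the problem without removing it.

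A reader might infer more than the texts support:

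- *That the two rules cannot both be followed.* They can, by stopping.
- *That cross-references elsewhere decide the matter, or can be tallied for each side.* Section 4.1.4.3 opens with "Treatment related toxicities will be managed by treatment interruptions and subsequent dose reductions of afatinib according to the schedule described in" the table, and Section 4.2.2 says "Pause the drug if applicable, refer to" it. Both concern pausing and dose reduction. Section 4.1.4.1 covers a reduced dose after recovery, and Section 2.3 only points to precautions. None addresses a child unrecovered at day 14.
- *That such a continuation would go unlogged because SAP deviation C3 names dose tables and not 4.2.1.* The tables stand in the comment/example column of a manually coded item. The item's description covers any handling not according to protocol.

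**Conclusion.** The inconsistency is real and confined to one situation: a child with a cardiac or LVEF event, unrecovered at 14 days, with obvious clinical benefit, for whom continuation is considered. There, continuing is allowed by footnote 2 and forbidden by Section 4.2.1.

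Its frequency is unknown and probably low. Protocol Section 1.2 reports no apparent adverse effect on cardiac contractility, and Section 2.3 says stringent monitoring in adults showed no impact on cardiac function. That the event is rare in children too is an assumption. It would be tempting to limit exposure to the expansion part because dose finding is complete. The documents do not show that dose-finding patients are off drug: courses are unlimited, and the figure of up to 38 counts evaluable patients, not treated ones.

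The conclusion rests on reading 4.2.1 as written. It does not depend on how item 6's undefined clinically relevant reduction is interpreted. This is a clarification of a safety rule that should be made, with no statistical consequence.

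**What to change.** Align the table with Section 4.2.1 and item 6, which already require stopping. Three edits in Section 4.1.4.3 do this:

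1. Remove the footnote 2 marker from the LVEF row.
2. Add to footnote 2: *does not apply to cardiac failure or LVEF decrease*. This keeps row 1 from reopening the exception.
3. Add to the sentence after the table on interruptions beyond 14 days: *cardiac failure and LVEF decrease follow the LVEF row*.

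Leave item 6 unchanged; tying it to the 14-day rule would loosen a discontinuation criterion without a stated reason.

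The cost is amendment wording, plus the loss of the case-by-case exception for a rare benefiting child. Whether that exception is worth keeping is the sponsor's clinical decision. If it is intended, it must be written into Section 4.2.1 and reconciled with item 6, including for diagnosed heart failure. Adding it to 4.2.1 alone would leave 4.2.1 and item 6 in conflict for that patient.

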4.2.2 Management of expected adverse events

At occurrence of a drug related AE:

- Pause the drug if applicable, refer to [Table 4.1.4.3:1](#)
- Treat the side effect
- Dose reduce at reintroduction if applicable

Dermatologic adverse events and diarrhoea are the most common side-effects associated with treatment with afatinib in the adult population. Treatment of these side-effects should be proactive and should be started as early as possible after onset of symptoms.

4.2.2.1 Management of diarrhoea and hydration status following treatment with afatinib

Diarrhoea occurs at a high frequency and generally begins within 2 weeks of exposure to afatinib. Although usually mild to moderate, diarrhoea may lead to dehydration and compel treatment modification or discontinuation, so early management is essential ([Table 4.2.2.1:1](#)). At the time of initiation of treatment with afatinib, patients/ parents/legal guardian should be given a supply of loperamide (if applicable) to keep with them at all times or access to loperamide (if applicable) should be confirmed; and patients/ parents/legal guardian(s) should be counselled on the appropriate use. In cases where loperamide is not available or approved

Proprietary confidential information.

© 2017 Boehringer Ingelheim International GmbH or one or more of its affiliated companies. All rights reserved.

This document may not - in full or in part - be passed on, reproduced, published or otherwise used without prior written permission.

for the age group institutional standards for treatment of “chemotherapy-associated diarrhoea” must be followed.

Maintaining fluid balance in children developing diarrhoea is crucial at all times to avoid dehydration and renal insufficiency. Investigators need to assure that parents are alerted to this and must describe early signs and symptoms of dehydration (dry mucosal membranes, crying without tears, fever, decrease in urine output) clearly to caregivers/patients. Also assure that caregivers understand diarrhoea is an afatinib associated side effect which requires treatment. Caregivers/patients must seek medical advice on occurrence of initial signs and symptoms of diarrhoea and complications thereof.

To maintain fluid balance, the patient’s fluid deficit must be assessed according to clinical standards. In addition daily fluid requirements may be estimated as 1.8L/m²/day, or more precisely 100 mL/kg/day can be calculated for the first 10 kg (1-10 kg). 50 mL/kg/day will be added for each kg body weight from 11-20 kg and 25 mL/kg/day can be calculated for each kg body weight from 20-30 kg. In addition estimated fluid deficits should be replaced within 36 hours, replacing the initial third of estimated fluid loss within 8-10 hours. CAVE: special rules apply for hypertonic dehydration ([R14-2337](#)).

Table 4.2.2.1: 1 Grade specific treatment recommendations for afatinib related diarrhoea

Severity (CTCAE Grading)	Description	Intervention concerning afatinib treatment	Specific intervention
Mild (Grade 1)	Increase of < 4 stools per day over baseline; mild increase in ostomy output compared with baseline	Continue same dose	Stop laxatives if any. Oral rehydration can be attempted, but i.v. fluid replacement should start quickly if oral rehydration is not effective. For oral rehydration, advise the patient/caregiver to assure fluid consumption of at least 1.8L/m ² electrolyte balanced fluids per day; in addition loperamide and racecadotril are preferred drugs for the treatment of diarrhoea. Treatment is to be started immediately according to the age-specific label instructions, i.e. for loperamide 0.4-0.8 mg/kg/24 h po should be applied at dose intervals of 6-12 hours until diarrhoea resolves; for chronic diarrhoea

Proprietary confidential information.

© 2017 Boehringer Ingelheim International GmbH or one or more of its affiliated companies. All rights reserved.

This document may not - in full or in part - be passed on, reproduced, published or otherwise used without prior written permission.

Table 4.2.2.1: 1 Grade specific treatment recommendations for afatinib related diarrhoea-(cont'd)

			0.5-1.5 mg/kg/24h po, given at dose interval of 6-12 hours, for maintenance reduce to 0.25-1 mg/kg/24 h po given at dose interval of 6-12 hours (R14-2354 , R14-2355) For racecadotril, where available, a dose of 1.5 mg/kg 3 times per day** proved very effective in stopping chronic diarrhoea (P13-10876 , P14-08260)
Moderate (Grade 2)	Increase of 4-6 stools per day over baseline; i.v. fluids indicated < 24 hours; moderate increase in ostomy output compared with baseline; not interfering with ADL	Continue same dose unless Grade 2 diarrhoea continues for ≥ 7 days in which case treatment must be interrupted until recovered to ≤ Grade 1 followed by dose reduction	Continue loperamide/ racecadotril as described above; assess degree of dehydration and electrolyte imbalance and consider i.v. fluid and electrolyte replacement early; an infectious process should be ruled out with stool cultures
Severe (Grade 3)	Increase of ≥ 7 stools per day over baseline; incontinence; IV fluids > 24 hours; hospitalization; severe increase in ostomy output compared with baseline; interfering with ADL	Dose interruption until recovered to ≤ Grade 1 followed by dose reduction*	See Grade 2; plus aggressive i.v. fluid replacement until fluid balance is restored; hospitalization to monitor progress; consider prophylactic antibiotics if patient is also neutropenic.
Life threatening (Grade 4)	Life-threatening consequences (e.g. haemodynamic collapse)	Dose interruption until recovered to ≤ Grade 1 followed by dose reduction*	See Grade 3

* If despite optimal supportive care and a treatment interruption, diarrhoea does not resolve to CTC AE Grade ≤ 1 within 14 days, treatment with afatinib must be permanently discontinued. In the event that the patient is deriving obvious clinical benefit according to the investigator's judgement, further treatment with afatinib will be decided in agreement between the sponsor and the investigator.

** Recommended for children of >3 months

4.2.2.2 Management recommendations for dermatological AEs following treatment with afatinib

Dermatologic AEs of afatinib include rash, acne, dermatitis acneiform and dry skin. General recommendations for prophylaxis are summarized in [Table 4.2.2.2: 1](#) and treatment recommendations specified by CTCAE grade are summarized in [Table 4.2.2.2: 2](#). For dose adjustment of afatinib refer to [Table 4.1.4.1: 2](#).

Specific interventions should be reassessed at each visit or at any worsening of symptoms, in which case the specific intervention should be adjusted and, depending on own clinical experience, early involvement of a dermatologist should be considered. (Adapted from [R11-0826](#))

Proprietary confidential information.

© 2017 Boehringer Ingelheim International GmbH or one or more of its affiliated companies. All rights reserved.

This document may not - in full or in part - be passed on, reproduced, published or otherwise used without prior written permission.

Table 4.2.2.2: 1 General recommendations for prophylaxis while receiving afatinib

Personal hygiene	
Use of gentle soaps and shampoos for the body, e.g. pH5 neutral bath and shower formulations and tepid water.
 
Use of very mild shampoos for hair wash.
 
Only clean and smooth towels are recommended because of potential risk of infection. The skin should be patted dry after a shower, whereas rubbing the skin dry should be avoided.
 
Fine cotton clothes should be worn instead of synthetic material.
 
Shaving (if applicable) has to be done very carefully.
 
Manicure, i.e. cutting of nails, should be done straight across until the nails no longer extend over the fingers or toes. Cuticles are not allowed to be trimmed because this procedure increases the risk of nail bed infections

Sun protection	
Sunscreen should be applied daily to exposed skin areas regardless of season. Hypoallergenic sunscreen with a high SPF (at least SPF30, PAPA free, UVA/UVB protection), preferably broad spectrum containing zinc oxide or titanium dioxide are recommended
 
Patients should be encouraged to consequently stay out of the sun.
 
Protective clothing for sun protection, sunglasses and wearing a hat should be recommended.

Moisturizer treatment	
It is important to moisturize the skin as soon as anti-ErbB therapy with afatinib is started.
 
Hypoallergenic moisturizing creams, ointments and emollients should be used once daily to smooth the skin and to prevent and alleviate skin dryness.
 
Note: avoid greasy creams (e.g. petrolatum, soft paraffin, mineral oil based) and topical acne medications

Prevention of paronychia	
Patients should keep their hands dry and out of water if possible.
 
They should avoid friction and pressure on the nail fold as well as picking or manipulating the nail.
 
Topical application of petrolatum is recommended around the nails due to its lubricant and smoothing effect on the skin.

Table 4.2.2.2: 2 Grade specific treatment recommendations of skin reactions to afatinib

Severity (CTCAE Grading)	Description	Specific intervention
ACNEIFORM RASH		
Mild (Grade 1)	Macular or papular eruptions or erythema without associated symptoms	
Consider referral to dermatologist.
 
Consider topical antibiotics, e.g. clindamycin 2% or topical erythromycin 1% cream or metronidazole 0.75% or topical nadifloxacin 1% as available, applicable and appropriately dosed for respective age group;
 
Isolated scattered lesion: cream preferred
 
Multiple scattered areas: lotion preferred

Moderate (Grade 2)	Macular or papular eruptions with pruritus or other associated symptoms; localized desquamation or other lesions covering <50% of	
Consider referral to dermatologist.
 
Topical treatment as for Grade 1 as available and applicable per age group plus short term topical steroids, e.g.

Proprietary confidential information.

© 2017 Boehringer Ingelheim International GmbH or one or more of its affiliated companies. All rights reserved.

This document may not - in full or in part - be passed on, reproduced, published or otherwise used without prior written permission.

Table 4.2.2.2: 2 Grade specific treatment recommendations of skin reactions to afatinib-
 (cont'd)

	BSA	prednicarbate cream 0.02% plus an oral antibiotic (for at least 2 weeks) e.g. erythromycin, clindamycin, minocycline hydrochloride as available, applicable and appropriately dosed for respective age group.
Severe (Grade 3)	Severe, generalized erythroderma or macular, popular or vesicular eruption; desquamation covering \geq 50% of BSA; associated with pain, disfigurement, ulceration or desquamation	Consult a dermatologist. Topical and systemic treatment as for Grade 2. Consider systemic steroids appropriately dosed for respective age groups. Assess fluid loss and replace fluid.
Life threatening (Grade 4)	Generalized exfoliative, ulcerative, or bullous dermatitis	Consult a dermatologist, hospitalize the patient, see also Grade 3 above. Systemic steroids are recommended appropriately dosed for respective age group. Assess fluid loss and replace fluid.
EARLY AND LATE XEROTIC SKIN REACTIONS – PRURITUS		
Mild (Grade 1)	Mild or localized	Consider referral to dermatologist Topical polidocanol cream. Consider oral antihistamines, e.g. diphenhydramine, dimethindene, cetirizine, levocetirizine, desloratidine, fexofenadine or clemastine) as available, applicable and appropriately dosed for respective age groups
Moderate (Grade 2)	Intense or widespread	Consider referral to dermatologist See Grade 1 plus oral antihistamines; Consider topical steroids, e.g. topical hydrocortisone as available, applicable and appropriately dosed for respective age group
Severe (Grade 3)	Intense or widespread and interfering with activities of daily living (ADL)	See Grade 2.
XEROSIS (DRY SKIN)		
Mild (Grade 1)	Asymptomatic	Consider referral to dermatologist Soap-free shower gel and/or bath oil. Avoid alcoholic solutions and soaps. Urea- or glycerin-based moisturizer. In inflammatory lesions consider topical steroids (e.g. hydrocortisone cream)
Moderate (Grade 2)	Symptomatic, not interfering with ADL	See Grade 1. In inflammatory lesions consider topical steroids (e.g. hydrocortisone cream)
Severe (Grade 3)	Symptomatic, interfering with ADL	See Grade 2. Topical steroids of higher potency (e.g. prednicarbate, mometasone furoate) Consider oral antibiotics as available,

Proprietary confidential information.

© 2017 Boehringer Ingelheim International GmbH or one or more of its affiliated companies. All rights reserved.

This document may not - in full or in part - be passed on, reproduced, published or otherwise used without prior written permission.

Table 4.2.2.2: 2 Grade specific treatment recommendations of skin reactions to afatinib-
 (cont'd)

		applicable and appropriately dosed for respective age group
FISSURES		
Mild (Grade 1)	Asymptomatic	Consider referral to dermatologist. Consider topical treatment as available, applicable and appropriately dosed for respective age group: e.g. petroleum jelly, Vaseline® or Aquaphor for 30 minutes under plastic occlusion every night, followed by application of hydrocolloid dressing; antiseptic baths (e.g. potassium permanganate therapeutic baths, final concentration of 1:10,000, or povidone-iodine baths); Topical application of aqueous silver nitrate solutions to fissures
Moderate (Grade 2)	Symptomatic, not interfering with ADL	See Grade 1. Consider oral antibiotics as available, applicable and appropriately dosed for respective age group.
Severe (Grade 3)	Symptomatic, Interfering with ADL	See Grade 2.
If Grade 2 rash persists for ≥ 7 days despite treatment and is poorly tolerated by the patient, the investigator may choose to pause treatment up to 14 days followed by a reduction in the dose of afatinib according to the dose reduction scheme in Table 4.1.4.3:1		

